23 COMMUNITY-BASED PARTICIPATORY RESEARCH

N/A.

24 MULTI-SITE RESEARCH

24.1 Communication and Protocol Approval at Multi-Site Centers

Roswell Park will be the IRB of record for this study. Accruals will occur at Roswell Park, Harvard School of Public Health (Site PI: [name]), and Medical University of South Carolina (Site PI: [name]). Each participating site will enter into a reliance agreement with the Roswell Park IRB, with appropriate inclusion of local information.

25 RESOURCES AVAILABLE

The PI has over a decade of experience in behavioral research. We are recruiting from the general population of Erie/Niagara. The total population over 21 is approximately 1 million, of which 15% smoke, we anticipate no issues in accruing 100 smokers.

26 PRIOR APPROVALS

This study is funded by National Cancer Institute. P01 CA217806 (PI: [name], University of Minnesota).

Roswell Park Protocol Number: I 757820

28 APPENDICES/ SUPPLEMENTS

Appendix A: Recruitment Materials

Print ad copy.

[insert site logo]

RESEARCH PARTICIPANTS NEEDED

Researchers at [insert study site] are searching for **smokers to participate in a two-week field study** for an important research project.

Participation involves two weeks of remote data collection and three videoconferencing sessions.
Remote data collection involves 5 daily questionnaires on product use.

Must be **21-69 years old daily cigarette smokers** to participate.
Participants will be compensated for their time.

If interested, please contact
[insert site contact number here]
And ask for the VENT study

Roswell Park Protocol Number: I 757820

Referral Coupon Example

VENT Study Coupon

Code:

Return of this coupon ensures the referrer to \$10
after the referral successfully completes the VENT Study

Date Distributed:

Date Returned:

Signed (Research Coordinator):

Roswell Park Protocol Number: I 757820

Prior Participant Recruitment Letter

[to be printed on [insert site]letterhead]

Dear *[insert name]*,

We are contacting you because you previously completed study with us, and asked to be contacted in the future if another research opportunity became available.

We are looking for regular cigarette smokers to participate in an important research project. The purpose of the study is to examine the impact of messaging about filter ventilation, a common design feature of cigarettes.

To do this, we are asking people to participate in a study involving two weeks of remote data collection and three videoconferencing sessions in which you will be asked to use specific cigarettes. During the first videoconference session, we would ask you to answer questionnaires on your smoking behavior and train you on remote data collection procedures. During remote data collection, we will ask you to respond to 5 questionnaires about product use, situational factors (location, social situation) and how you're feeling. We hope findings from this study can inform the regulation of cigarette products by the federal or state government.

This research has received ethics clearance from the Roswell Park Institutional Review Board and all the information you provide will be kept strictly confidential. Only the investigators directly associated with the study will have access to this information. This study is funded by the National Cancer Institute, National Institutes of Health, and the investigators have no affiliations with any tobacco or pharmaceutical company.

If you are interested, please contact *[insert site contact number]*, and ask for the VENT Study. You may also email *[insert site email]* with a good time to call you.

Sincerely,

[insert name]
[insert title] [insert location] [insert study site]

Roswell Park Protocol Number: I 757820

Appendix B: Eligibility Screener

Core Eligibility Screener

1. Please enter your name.

2. Please enter your phone number, starting with the area code.

3. Do you currently use tobacco products? By currently, we mean any use at all in the last month (30 days)

Yes
 No

4a. Which products have you used in the past 30 days? Please check all that apply.

Cigarettes (proceed to 4b)
 Cigars
 Cigarillos
 Clove Cigarettes
 Herbal Cigarettes
 Bidis
 Pipe Tobacco
 Roll Your Own
 Chewing Tobacco
 Moist Snuff
 Snus
 E-Cigarettes
 Vapes
 No products. I am not a smoker. (Ineligible)

4b. Are your current cigarettes made by a company or roll your own?

Manufactured
 Roll Your Own

5. Which brand of cigarettes do you currently smoke? Please be as specific as possible (e.g. Marlboro gold 100s box).

(needs to smoke factory-made filtered cigarettes)

Note to interviewer: check brand variety against lab database. Eligible if ventilation >10%. Common ineligible brands: Newport menthol; Newport red; Marlboro Black. If data unavailable, ask participant to bring a pack of their own cigarettes to Session 1 for confirmation.

Roswell Park Protocol Number: I 757820

6. Have you used any Nicotine Replacement medication such as the patch, gum, lozenge, spray, or inhaler in the past 30 days?

Yes

No

7. Do you smoke cigarettes some days or every day?

Every Day

Some Days

Not at all

8. How many cigarettes do you smoke per day? Please enter a number.

5 or more

Less than 5

9. How long have you been smoking?

More than 1 year

Less than 1 year

10. Have you tried to quit smoking in the past 30 days?

(More than a 24-hour time period without smoking)

Yes

No

11. Are you seriously thinking of quitting smoking?

Yes, within the next 30 days

Yes, within the next 6 months

No, not thinking of quitting

12. What sex do you identify with?

Male

Female

Undetermined

Refused

13. What is your age? Please enter a number (years).

(Eligible = 18-69 years old)

14. Please describe your overall health.

Excellent

Very Good

Good

Fair

Poor

Roswell Park Protocol Number: I 757820

15. Please describe your overall mental health.

Excellent
 Very Good
 Good
 Fair
 Poor

16a. How often did you have a drink containing alcohol in the past year?

Never (0)
Monthly or less (1)
Two to four times a month (2)
Two to three times a week (3)
Four or more times a week (4)

16b. How many drinks did you have on a typical day when you were drinking in the past year?

None, I do not drink (0)
1 or 2 (0)
3 or 4 (1)
5 or 6 (2)
7 to 9 (3)
10 or more (4)

16c. How often did you have six or more drinks on one occasion in the past year?

Never (0)
Less than monthly (1)
Monthly (2)
Weekly (3)
Daily or almost daily (4)

16total. Sum responses to 16a-c (score must be <7 for inclusion)

17. How many times in the past month have you consumed cannabis/marijuana/THC?

(>5 = Ineligible)

18. How many times in the past month have you used an illegal drug or used a prescription medication for non-medical reasons? Please enter the number below.

(>1 = Ineligible)

19. Are you currently involved in any other Roswell Park research studies?

Yes (place on wait list if otherwise eligible; can begin after involvement in other study ends)
 No

These next few questions ask about rules of using tobacco inside your home. Please think about everyone who might be in your home including children, adults, visitors, guests, or workers. For tobacco products that are burned, such as cigarettes, cigars, pipes or hookah, which statement best describes the rules about smoking a tobacco product inside your home?

Roswell Park Protocol Number: I 757820

- 1 It is not allowed anywhere or at any time inside my home
- 2 It is allowed in some places or at sometimes inside my home
- 3 It is allowed anywhere and at any time inside my home

For electronic cigarette products, such as e-cigarettes, vape pens, tanks, mods, JUUL, which statement best describes the rules about vaping inside your home?

- 1 It is not allowed anywhere or at any time inside my home
- 2 It is allowed in some places or at sometimes inside my home
- 3 It is allowed anywhere and at any time inside my home

If Ineligible:

Unfortunately, you are ineligible for the study. However, we thank you for your interest and hope you have a great day.

If Eligible:

You are eligible for the study! I'd like to give you some more information before asking whether you'd like to participate. The purpose of the study is to examine the relationship of certain cigarette design features, such as pack messages, to exposure and consumer perceptions. You will be asked to take part in a two-week field experiment where you will be assigned to smoke specific cigarettes and track your use. The study is done remotely, so we will send you all study materials and text/email questionnaires to you. Three times during the field experiment, you will be asked to videoconference with a research assistant for approximately 30 minutes. In addition, you will be asked to respond to 5 brief questionnaires daily to track your cigarette use and report on study cigarettes.

This project has received ethics clearance from the Roswell Park Comprehensive Cancer Center Institutional Review Board and all the information you provide will be kept strictly confidential. Only the investigators directly associated with the study will have access to this information and it will be destroyed once the study is completed.

I realize I've given you a lot of information- do you have any questions about the study?

Would you like to participate in the study?

If no: Thank you and goodbye.

If yes: Great.

We'd like to get your mailing address and email address so we can send you additional information about the study. Are you willing to provide one or both?

Mailing Address:

Roswell Park Protocol Number: I 757820

Email:

What day(s) would be the best to reach you? Please check all that apply.

- Monday
- Tuesday
- Wednesday
- Thursday
- Friday
- Saturday
- Sunday

What time of day would be best to reach you? Please check all that apply.

- Morning (8am – 12pm)
- Afternoon (12pm – 4pm)
- Evening (4pm – 8pm)

Roswell Park Protocol Number: I 757820

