7 INCLUSION AND EXCLUSION CRITERIA

7.1 How Individuals Will Be Screened For Eligibility

We will recruit adult smokers for the study via community contacts, ad postings in local daily, weekly, and college newspapers, websites such as Craigslist and Facebook, and local tobacco control networks (methods we have previously used to recruit successfully, cf. ^{71,152,153}).

Screening methods may involve live telephone interviews, automated telephone screeners (via IVR), and online screening methods where the recruit will complete an eligibility screener online and receive a callback for scheduling pending eligibility.

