7.2 Inclusion Criteria

1. Aged 21-69 years old.
2. Currently smoking daily, at least 5 cigarettes per day, for the past year:
 - a. Primarily using factory-made filtered cigarettes.
3. Fair and above self-rated physical health (self-rated).
4. Fair and above self-rated mental health (self-rated).
5. Not planning to quit smoking in the next 30 days.
6. Able to converse, read, and write in English.
7. Access to smartphone (e.g., iPhone, Android) for Ecological Momentary Assessment (EMA) component.
8. Access to a smartphone/tablet/computer with video capabilities and internet access for remote videoconferencing (EMA check-ins).
9. AUDIT-C score <7 (i.e., no problematic alcohol consumption).
10. Cannabis use ≤ 5 days in the past month.
11. No other illegal drug use in the past month (allow for prescriptions).
12. Not pregnant or breastfeeding or planning to become pregnant during the study period.
13. Participant must understand the investigational nature of this study and sign an Independent Ethics Committee/Institutional Review Board approved written informed consent form prior to receiving any study related procedure.

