7.3 Exclusion Criteria

1. Age < 21 or > 69 .
2. Using roll-your-own cigarettes or usual brand of cigarettes is unfiltered.
3. Planning to quit smoking in the next 30 days.
4. Not able to converse, read, and write in English.
5. Adults unable to consent.
6. Minors (any persons under age 21).
7. Prisoners.
8. Poor physical health by self-report.
9. Poor mental health by self-report:

Roswell Park Protocol Number: I 757820

- Exclude Dx psychosis, Dx bipolar, K6 score indicating serious psychological distress.
- 10. AUDIT-C score ≥ 7 (i.e. problematic alcohol consumption).
- 11. Cannabis use >5 days in past month.
- 12. Other illegal drug use in past month.
- 13. Pregnant or breastfeeding by self-report.
- 14. No access to smartphone or videoconferencing.

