7.5 Special Populations

The following populations will be excluded from study participation:

- Cognitively impaired adults/adults with impaired decision-making capacity
- Individuals who are not yet adults (infants, children, teenagers)
- Pregnant Women
- Prisoners

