Please keep track of the amount of cigarettes and other tobacco you use. The scheduled prompts will ask you to report the number of cigarettes you've smoked. The random prompts will ask you to report on the situation in which you last used your product, such as the location and if smoking was allowed. We also ask that you store all used cigarette butts in the provided materials

Here are examples of the questions you will be asked at each assessment (show questionnaires). Do you have any questions?

We are also providing you with a CO monitor that will connect with your phone to take a CO measurement each night (demonstrate use).

We are also providing you with a scale to weigh other tobacco products that you may use, such as an e-cigarette or smokeless tobacco. If you use these other products, we would like you to weigh your product (e.g., pod, tank, dip tin) at the beginning and end of each day. If you are close to finishing your product and may start a new one, please weigh both the older and newer one at the beginning and end of the day.

Two additional times during the field study, we will ask you to videoconference with us as a study check-in and to have you respond to some questionnaires.

These are the cigarettes we are asking you to use during the field study (provide research cigarettes). Please use only these cigarettes and do not tamper with the cigarette pack. At random points in the study, we may ask you to take a picture of the cigarette pack.

Do you understand the procedures for the field study? Please call us if you have any questions.

Videoconferencing Sessions 2 & 3

Hello, today we are going to have you fill out a questionnaire. I will send it to you now. Have you been regularly storing your cigarette butts. Can I see how you are storing them?

Compliance: Your compliance has been great. Thank you!

Or: Your compliance has not met the standards. Please respond to more prompts or you may be discontinued for the study. Do you have any questions about the study procedures that may help you respond to more prompts?

Session 3 only:

Please pack up your supplies to prepare a return shipment. Can I see how you've stored your supplies in the box?

When we receive your materials, we will send you payment for completing the study. Thank you for participating.

Roswell Park Protocol Number: I 757820

Ads for the website/mobile app:

RESEARCH PARTICIPANTS NEEDED

Searching for:
21-69 year old daily cigarette smokers

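### Appendix B's screener passes ages 18 to 20, which Sections 7.2 and 7.3 exclude, and no later age check is tied to the protocol limit or to a time before cigarette supply

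*Combined protocol and SAP*

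**What the plan says.** The body of the protocol is consistent on age:

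- Section 7.2, inclusion criterion 1: "Aged 21-69 years old".
- Section 7.3, exclusion criterion 1, removes anyone below 21 or above 69. Exclusion criterion 6 gives the reason for the lower limit: "Minors (any persons under age 21").
- Section 7.5 lists among the excluded populations "Individuals who are not yet adults (infants, children, teenagers").
- The print advertisement in Appendix A asks for "21-69 years old daily cigarette smokers", and the web and mobile advertisement text at the end of Appendix D asks for "21-69 year old daily cigarette smokers".

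Appendix B, item 13, asks for age in years and instructs "Eligible = 18-69 years old". No other screener item asks about age. A recruit who meets the items is told "You are eligible for the study".

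Sections 7.1 and 8.2 allow the screener to be run by live telephone interview, by automated telephone line, or online. In the online route the recruit will "complete an eligibility screener online and receive a callback for scheduling pending eligibility".

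**The concern.** The screener is where the age rule is first applied to a recruit, and two of its three permitted modes can run without staff judgement. A wrong threshold there is wrong in use, even though the criteria in Section 7 are clear.

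The product supplied is cigarettes, and the people wrongly passed are ones the protocol itself classes as minors, so the first issue is participant protection. The second is statistical and smaller. An under-21 discovered after randomisation is an eligibility violation, and Section 22.1 has no rule for keeping or removing such a participant.

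Under-21s could plausibly reach the screener. Sections 6.1.1, 7.1 and 8.1 include college newspapers among the recruitment channels. The referral coupon, the letter to prior participants and one of the banner advertisements state no age. For someone arriving by those routes, item 13 is the first age limit the documents show.

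**Working it through.** No sample size, power or alpha figure enters this point. The check sets the age rules side by side and then follows a recruit through the described steps.

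**Age rules**

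| Place | Lowest age accepted | Highest age accepted |
|---|---|---|
| Section 7.2, inclusion 1 | 21 | 69 |
| Section 7.3, exclusions 1 and 6 | 21 | 69 |
| Advertisements that state an age (Appendices A and D) | 21 | 69 |
| Appendix B, item 13 | 18 | 69 |

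- Single-year ages accepted by the screener: 69 − 18 + 1 = 52.
- Single-year ages accepted by Sections 7.2 and 7.3: 69 − 21 + 1 = 49.
- Difference: 52 − 49 = 3, namely ages 18, 19 and 20. The upper limits agree.

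Section 7.5 names teenagers, which covers 18 and 19 but not 20. The exclusion of all three ages therefore rests on Section 7.3.

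**Path of a 19-year-old who meets every other screener item**

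1. Item 13 as printed is satisfied, and the eligible script is read (Appendix B).
2. A call to schedule follows (Sections 7.1 and 8.2).
3. Consent is taken by videoconference (Sections 9.1 and 11.3).
4. Randomisation to one of the four message conditions follows consent (Section 11.3).
5. Study materials, including cigarettes, are mailed, delivered or collected (Section 11.3).
6. Session 1 takes place once the materials have arrived (Section 11.3). Age is asked again in the demographics questionnaire in Appendix C, which belongs to the baseline intake at this session.

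**Checks that might intervene**

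- Date of birth is collected to verify age (Sections 19.1 and 21.1). Neither section gives a time, a limit or an action on failure. Staff working from Appendix B could check it against 18.
- Signature on delivery (Section 13.1) confirms that the right person has received a mailed parcel. It does not establish age.
- The questionnaire at step 6 comes after supply.

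No step before supply is therefore documented as applying the limit of 21.

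**The case against.** The strongest reply is that passing the screener supplies nobody with cigarettes. It leads to a scheduling call, and staff-led consent and randomisation come before any shipment. Date of birth is already collected for the stated purpose of verifying age. The screener also cannot be the whole eligibility decision: as printed it has no item on pregnancy or breastfeeding, the K6 score, a diagnosis of psychosis or bipolar disorder, or access to a smartphone and video. Some confirmation must happen elsewhere. The governing criteria are unambiguous, and most of the advertising already says 21 to 69.

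Much of this stands, and it limits what can be claimed:

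- A reader might infer that the study will randomise under-21s and send them cigarettes. The documents do not support that. They show that it could happen if the age check is missing, late, or made against 18.
- A reader might want to put a number on it by applying an assumed percentage to the 300 planned participants. The documents give no age distribution of recruits and no failure rate for the later check, so any such count would be invented. An 18- to 20-year-old must also meet the smoking criteria, including daily smoking of at least 5 cigarettes for more than a year (items 7 to 9).
- A reader might infer that the live automated or online form uses 18. Only the printed text of Appendix B is available, so the setting in the build is unknown.

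The reply does not remove the contradiction. The later confirmation of eligibility is not described. The one deferred check that Appendix B does describe, confirming an unlisted cigarette brand, is placed at Session 1, after the materials have been received.

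**Conclusion.** The concern holds as an internal inconsistency. Item 13 is wrong as written against Sections 7.2 and 7.3, and nothing in the document reconciles it. Its size is three single-year ages: 18, 19 and 20. The number of people affected is unknown and cannot be derived.

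The consequence is conditional. Otherwise qualifying recruits of those ages could reach consent, randomisation and cigarette supply unless the date-of-birth check catches them, and that check has no stated timing or limit. This rests on reading item 13 as the rule the screener applies, and on there being no age verification procedure beyond what the protocol describes.

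The intended limit is not in doubt, because item 13 is the only place that departs from 21. No estimand, endpoint, power figure or analysis changes. The case for correcting it before use is participant protection and avoidable eligibility violations.

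**What to change.** 1. In Appendix B, change the age rule in item 13 to 21-69, matching Sections 7.2 and 7.3.
2. Confirm that any automated telephone or online version of the screener uses the same limit, and correct it if it does not.
3. In Section 11.3, with a cross-reference from Sections 19.1 and 21.1, state that the existing date-of-birth check is made against 21-69 before randomisation and before any materials are shipped or handed over. State also that a recruit who fails it is not enrolled.

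If screening has already used the printed item, compare the dates of birth on file with the limit of 21.

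The cost is one figure in an appendix, one check of the screener build and a sentence or two on a step that is already planned. No new data are collected, and the sample size and analysis are untouched.

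### Screener items 17 and 18 do not implement the Section 7 drug and cannabis criteria: one illegal-drug use passes, and cannabis is counted in times rather than days

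*Combined protocol and SAP*

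**What the plan says.** Sections 7.2 and 7.3 state each rule twice, and the two statements agree.

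- **Illegal drugs.** Inclusion criterion 11 reads "No other illegal drug use in the past month", with an allowance for prescriptions. Exclusion criterion 12 reads "Other illegal drug use in past month". Both mean zero use, and both use the word *other*, which sets cannabis aside for its own rule.
- **Cannabis.** Inclusion criterion 10 reads "Cannabis use ≤ 5 days in the past month". Exclusion criterion 11 reads "Cannabis use >5 days in past month". The unit is days.

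The Appendix B screener puts the same matters differently.

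- **Item 17** asks "How many times in the past month have you consumed cannabis/marijuana/THC", with the cut-off ">5 = Ineligible". The unit is times.
- **Item 18** asks how often, over the same month, the person took an illegal drug or took a prescription medicine non-medically. Its cut-off is ">1 = Ineligible".

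**The concern.** A screener should give the same answer as the criteria it stands in for. Here it differs at two thresholds that decide who enters the study. The cut-off in item 18 is looser than Section 7, so a person whom the written criteria exclude may be enrolled, which would be an avoidable protocol deviation. Item 17 is stricter, so an eligible smoker may be turned away.

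The screener's wording matters because Sections 7.1 and 8.2 allow automated telephone and online screening, where a coded cut-off may be applied without an interviewer's judgement. The Session 1 intake (Section 11.3), the baseline measures (Section 11.4) and the Appendix C questionnaires contain no further question on drugs or cannabis, so no documented step would catch an error made here.

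**Working it through.** No figure in the plan needs reproducing. The check sets each criterion beside its screener item and tests the boundary values.

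**Item 18, illegal drugs.** Inputs: criteria 11 (7.2) and 12 (7.3), and the item 18 cut-off. Take the number of uses of an illegal drug other than cannabis, with no cannabis and no non-medical prescription use, so that scope does not interfere.

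| Uses in the past month | Section 7 | Item 18 |
|---|---|---|
| 0 | eligible | passes |
| 1 | excluded | passes |
| 2 or more | excluded | excluded |

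The cut-offs disagree at exactly one value, and there the screener admits someone Section 7 excludes.

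**Item 18, scope.** Two features mean that the item does not measure the Section 7 criterion one-to-one.

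- It omits *other*. A respondent with permitted cannabis use may count it. One such use gives an answer of 1, which breaches nothing; two or more would be screened out at item 18 although Section 7 allows them.
- It pools in non-medical use of prescription medicines. Section 7 makes an allowance for prescriptions and does not say whether non-medical use counts.

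So an answer of 1 is not by itself proof of ineligibility, and the scope problem can turn away people whom Section 7 does not clearly exclude.

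**Item 17, cannabis.** Let D be the days with any cannabis use in the past month and T the number of times used. Each day of use has at least one use, so T ≥ D.

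| Case | Section 7 (by D) | Item 17 (by T) |
|---|---|---|
| D > 5, hence T > 5 | excluded | excluded |
| T ≤ 5, hence D ≤ 5 | eligible | passes |
| D ≤ 5 and T > 5 | eligible | excluded |

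Only the third row disagrees. Illustration: 3 uses on each of 2 days gives T = 3 × 2 = 6, which is above 5 and fails item 17, while D = 2 is within the limit of 5 days. Because D > 5 forces T > 5, item 17 admits nobody whom the cannabis criterion excludes.

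**The case against.** The strongest reply is that Appendix B is not the whole eligibility check. It has no item on pregnancy or breastfeeding, diagnosed psychosis or bipolar disorder, psychological distress on the K6, or smartphone and video access, all of which Section 7 requires; the K6 appears only in Appendix C. Staff may therefore work from the Section 7 list as well. That stands as far as it goes, and it is why the consequence is that an ineligible person *may* be enrolled. It does not remove the contradiction, because no second drug question is shown. Nor is the screener plainly a coarser pre-screen: its AUDIT-C limit matches Section 7 exactly.

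A second reply is that respondents may read the items as intended, taking times as days in item 17, or treating item 18 as excluding cannabis because the cannabis question comes just before it. Some may, but nothing in the wording ensures it, and neither reading changes the item 18 cut-off.

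A reader might also infer more than the documents support:

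- *Everyone who answers 1 at item 18 is ineligible.* Not so, given the pooled scope shown above.
- *Accrual to 300 will suffer.* No frequency of cannabis use is given, and Section 25 expects no difficulty recruiting the 100 local participants. That statement covers one area only, but nothing points the other way.
- *The comparison of message arms is biased.* Under Section 11.3 randomisation follows screening and consent, so the mismatch does not itself favour any arm.

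**Conclusion.** The point holds as a minor internal inconsistency between Appendix B and Section 7. It is not an arithmetic error. The item 18 cut-off is one unit too loose against a zero-use criterion, its scope differs from that criterion, and item 17 uses a stricter unit than the cannabis criterion.

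The size cannot be stated in numbers: the documents do not say how many screenees would report exactly one illegal-drug use, or more than 5 cannabis uses on 5 or fewer days. What is exposed is adherence to the written criteria and the description of who was enrolled. No endpoint, error rate or sample-size figure depends on it.

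The conclusion assumes that the screener is applied as printed and that respondents count uses literally. The documents do not establish whether Section 7 or the screener reflects the intended rule.

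**What to change.** Reconcile Appendix B with Section 7 so that unit, scope and cut-off agree.

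**If Section 7 stands as written:**
- Item 17 should ask on how many days in the past month cannabis was used, with more than 5 days ineligible.
- Item 18 should ask about illegal drugs other than cannabis, with 1 or more uses ineligible. The scope must change together with the threshold: tightening the cut-off on the present pooled question could reject people whose only use was permitted cannabis.
- Section 7 should state whether non-medical use of prescription medicines counts. If it does, it may stay in item 18; if not, it should come out.

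**If the screener's rules were intended,** amend Sections 7.2 and 7.3 instead.

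The cost is a few words and one threshold in Appendix B and in the telephone and online versions of the screener, plus one clarifying phrase in Section 7. The same edit could settle item 13, which marks ages 18-69 as eligible where Section 7.2 requires 21-69.
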